#### **6.5. Concurrent medication**

**6.5.1. Pre-trial medicines:** There are no restrictions on concurrent medication on entry to the run-in phase.

**6.5.2. Folic acid:** Folic acid (prescribed and over-the-counter preparations) should also be stopped (unless there are reasons why the participant should not be randomised to folate/placebo [see section 4.1.2.]).

**6.5.3. Carbamazepine:** Carbamazepine (which decreases the serum level of lamotrigine) should be stopped during the run-in phase or replaced by oxcarbazepine.

**6.5.4. Other psychotropic medicines:** Investigators will be encouraged to consider withdrawing any other treatments for mood symptoms that participants were taking prior to entry to the run-in phase but these drugs can be continued where clinically indicated. Drugs that are not withdrawn should be continued at the same dose for the duration of the trial unless there is a clinical need for change. All concurrent psychotropic medicines should be recorded on the baseline assessment form and any subsequent changes reported.

**6.5.5. Rescue medication:** Investigators will be asked to avoid altering the dose of quetiapine during the first 12 weeks of the randomised phase. Emergent psychotic symptoms should be treated with an alternative antipsychotic (e.g. risperidone) and agitation should be treated with short courses of benzodiazepines.

**6.5.6. Additional treatment for depressive symptoms:** Investigators will be asked not to prescribe any additional treatment for depressive symptoms during the first 12 weeks of the randomised phase. After 12 weeks, new treatment for depressive symptoms can be initiated as clinically appropriate if response to allocated treatment is considered to be inadequate or if new symptoms emerge.

## **6.6. Supply of trial treatments**

**6.6.1. Lamotrigine and matching placebo:** Lamotrigine and matching placebo will be donated by/purchased from GSK according to the contract agreed by GSK and the University of Oxford.

**6.6.2. Folic acid and matching placebo:** Folic acid and matching placebo will be donated by Recip.

## **6.7. Packaging, labelling and accountability of trial treatments**

All tablets will be packaged by a clinical trial supplies packaging company and delivered to the Oxfordshire and Buckinghamshire Mental Health Partnership NHS Trust Pharmacy. All movements of trial medicines between manufacturer, packaging company and pharmacy will be documented. Qualified Person (QP) release will be provided by the packaging company.

**6.7.1. Packaging:** The clinical trials packaging company will be provided with 6 lists of pack numbers – one for each tablet size of active lamotrigine (i.e. 25mg and 100mg), one for the same tablet sizes of lamotrigine placebo, one for active folic acid (500µg tablets) and one for matching folic acid placebo tablets. The numbers will be generated by the CEQUEL computer programmers and stored directly in a restricted-access database table. When a participant enters the randomised phase, the computer program will generate a list of numbers which correspond to the appropriate allocation and planned lamotrigine/placebo dose for the first packs of trial medicines to be sent. The numbers for subsequent packs of medication will be generated as required in the same way.

**6.7.2. Prescription of lamotrigine:** The first prescription for lamotrigine/placebo will cover medication for up to 6 months. The medication will be sent out in quantities that cover four or eight week periods. The first pack will be sent after randomisation. The second pack will be sent 2 weeks later. This will establish a 2-week overlap between packs. Thereafter packs will be sent at 4-week intervals for the first 12 weeks and then at 8-week intervals for the remainder of the six-month period.

Twenty-two weeks (5 months) after randomisation, the investigator will be asked to complete a new prescription form for lamotrigine/placebo for weeks 27 to 52 to ensure continuity of treatment. This medication will be sent out in 8-week packs.

If the dose of lamotrigine is altered at any time and the new dose is protocol compliant, the investigator will be required to complete a new prescription form which will supersede all previous forms for the remainder of the six-month period. The investigator will be asked to specify whether the change should be effected immediately or when the next pack is sent. If the new dose is not protocol compliant the supply of trial medicines will be stopped and the investigator will be asked to arrange for treatments to be supplied locally.

**6.7.3. Prescription of folic acid:** The first prescription for folic acid/placebo will cover medication for 6 months. The medication will be sent to the participant after randomisation. The investigator will be asked to complete a second prescription after 22 weeks (5 months) of treatment and a second pack containing enough folic acid for 6 months will be sent out after 24 weeks (5 ½ months).

**6.7.4. Dispensing trial medicines:** A Service Level Agreement will be set up between the Department of Psychiatry CEQUEL Office and the Oxfordshire and Buckinghamshire Mental Health NHS Trust Pharmacy to cover dispensing of medicines, re-ordering of stock, checking of expiry dates etc.

The list of pack numbers assigned to a participant for a new supply of medicines (see section 6.7.1.) will be sent to the trial pharmacy by encrypted email together with a passworded letter to the participant. The pharmacy will print a copy of the letter, dispense the treatments and mail them to the participant at their home address, or other address agreed with the participant, investigator and proposed recipient. Packages of medication will usually be sent by Royal Mail Recorded Delivery to facilitate tracking of packages. When this is not appropriate, first class mail or courier services will be used. Participants will be required to acknowledge receipt of each package before a subsequent package is sent. If receipt is not confirmed and the participant cannot be contacted, authorisation to send the next package will be sought from the investigator. When required, participants will be provided with Freepost labels to return any unwanted trial medicines to the trial pharmacy.

The pack labels will contain all the information required by law and will be agreed with the Medicines and Healthcare products Regulatory Agency.

## **7. Blood Tests**

### **7.1. Timing of blood samples**

Participants will be asked to give a blood sample (approximately 10ml.) at the screening appointment and again at the 12-week follow-up appointment.

## 7.2. Obtaining blood samples

Investigators will be provided with blood collection tubes that can be used to collect samples for homocysteine assay and serum tests. Investigators will also be provided with packaging so that the samples can be mailed to the CEQUEL office. At the screening appointment the investigator should either take the blood samples or arrange for the samples to be taken before randomisation.

## 7.3. Storage and analysis of blood samples

On receipt at the CEQUEL office, samples will be taken to the Department of Neurosciences where they will be centrifuged. The serum will be sent to the Department of Physiology Anatomy and Genetics where the biochemical tests will be performed. The test results will be available within 2 months of receipt of the sample. The remainder of the samples will be retained in Neurosciences for genotyping.

## 7.4. B12 deficiency

In the unlikely event that a participant is found to be B12 deficient (defined as serum level below 150pmol/L), the investigator will be informed and advised about the need for the participant to be prescribed B12 supplementation. No other blood test results will be reported to investigators.

## 8. Assessment of Safety

(See Appendix 2: Classification of adverse events)

### 8.1. Definitions

**8.1.1. Adverse Event (AE):** Any untoward medical occurrence in a trial participant administered a medicinal product, which does not necessarily have to have a causal relationship with this treatment (the trial medication).

An AE can therefore be any unfavourable and unintended sign (including an abnormal laboratory finding), symptom or disease temporally associated with the use of the trial medication, whether or not considered related to the trial medication.

**8.1.2. Adverse Reaction (AR):** All untoward and unintended responses to a medicinal product related to any dose. Response is taken to mean that a causal relationship between a trial medication and an AE is at least a reasonable possibility, i.e., the relationship cannot be ruled out.

**8.1.3. Serious or Severe Adverse Events:** To ensure no confusion or misunderstanding of the difference between the terms "serious" and "severe", which are not synonymous, the following note of clarification is provided:

The term "severe" is often used to describe the intensity (severity) of a specific event (as in mild, moderate, or severe myocardial infarction); the event itself, however, may be of relatively minor medical significance (such as severe headache). This is not the same as "serious," which is based on patient/event outcome or action criteria usually associated with events that pose a threat to a patient's life or functioning. Seriousness (not severity) serves as a guide for defining regulatory reporting obligations.

**8.1.4. Serious Adverse Event or Serious Adverse Reaction:** A serious adverse event or reaction is any untoward medical occurrence that at any dose:

- results in death
- is life-threatening (see note below)
- requires inpatient hospitalisation or prolongation of existing hospitalisation,
- results in persistent or significant disability/incapacity, or
- Is a congenital anomaly/birth defect.

**NOTE:** The term "life-threatening" in the definition of "serious" refers to an event in which the patient was at risk of death at the time of the event; it does not refer to an event which hypothetically might have caused death if it were more severe.

Medical and scientific judgment should be exercised in deciding whether an adverse event is serious in other situations.

**8.1.5. Suspected Unexpected Serious Adverse Reactions (SUSARs):** A serious adverse reaction, the nature or severity of which is not consistent with the applicable product information (e.g., Investigator's Brochure for an unapproved investigational product or pack insert/summary of product characteristics for an approved product).

**8.1.6. Assessment of causality:** All cases judged by either the reporting medically qualified professional or the sponsor as having a reasonable suspected causal relationship to the trial medication qualify as adverse reactions.

## **8.2. Serious Adverse Event Reporting Procedures**

**8.2.1. Reporting by investigator:** All SAEs, except those SARs that do not require immediate reporting (see 8.2.3.), must be reported to the Chief Investigator (CI) within one working day of discovery or notification of the event. All SAE information must be recorded on an SAE form and emailed/faxed to the CI. Additional information received for an event (follow-up or corrections to the original event data) need to be detailed on a new SAE form and sent/faxed to the sponsor.

In addition to SAE reporting, investigators should report to the CI any non-serious adverse reactions that they consider to be unexpected or for which they consider the severity or duration to be greater than that indicated in the Summary of Product Characteristics (SmPC). Adverse events that lead to withdrawal from the run-in phase or termination of any of the trial treatments during the randomised phase should also be reported.

Investigators are not required to report other non-serious adverse events.

**8.2.2. Reporting by the Chief Investigator:** The CI will:

- report all SUSARs to the Competent Authorities (MHRA in the UK) and the REC concerned. Fatal or life-threatening SUSARs must be reported within 7 days and all other SUSARs within 15 days
- report all SAEs (including SUSARs) to the participant's NHS Trust and to the IDMEC
- inform all investigators concerned of relevant information about SUSARs that could adversely affect the safety of participants.

In addition to the expedited reporting above, the CI will:

- submit once a year throughout the clinical trial or on request a safety report to the Competent Authority (MHRA in the UK), the main REC and participating NHS Trusts and send a copy to the University of Oxford Clinical Trials Research Governance Team.
- provide data on all reported AEs to the IDMEC as required.

**8.2.3. Expected Serious Adverse Reactions:** Immediate reporting of Suspected Serious Adverse Reactions that are listed in the SmPC for the appropriate trial treatment(s) will not be required provided that the severity and seriousness are consistent with the information given in the SmPC.

**8.2.4. Other expected Serious Adverse Events**

Immediate reporting of the details of hospital admission to treat mood episodes will not be required.

**8.3. Reporting Procedures for all Adverse Events**

All SAEs whether observed by the investigator or reported by the participant and whether attributed to trial medication or not, will be reported in the CRF. SAEs considered by the investigator or the CI to be related to the trial medication will be followed until resolution or until the event is considered stable. The following attributes must be assigned by the investigator: description, date of onset and resolution date, severity, assessment of relatedness to trial medication, other suspect drug or device and action taken. The investigator may be asked to provide follow-up information.

It will be left to the investigator's clinical judgment whether or not an SAE is of sufficient severity to require the participant's removal from treatment. A participant may also voluntarily withdraw from treatment due to what he or she perceives as an intolerable AE.

All SAEs that are related to trial medicines or trial procedures and either result in a participant's withdrawal from the trial or are present at the end of the trial should be followed up until symptoms cease or the condition becomes stable.

All deaths occurring on trial must be reported to the CI. These include deaths within 30 days of the final dose of trial medication and deaths up to the last formal follow-up observational period, whichever is longer. For all deaths, available autopsy reports and relevant medical reports will be requested for reporting to the relevant authorities.

Any pregnancy occurring during the trial and the outcome of the pregnancy should be reported to the Chief Investigator.

---

 The severity of events will be assessed on the following scale:  
1 = mild, 2 = moderate, 3 = severe.

## 9. Statistics

### 9.1. Analyses

The principal comparisons (outlined in section 2.1) will be performed on an intention-to-treat basis. The results from the trial will be presented as comparative summary statistics with 95% confidence intervals. Continuous outcomes: To address the principal research questions (see section 2.1), an analysis at the margins will be conducted (McAlister, 2003). Depending on the distribution of the continuous outcome measures, if appropriate, a mixed effect model will be used to analyse QIDS-SR16 collected over 12 months. Treatment-time interaction will be included in the model to assess the treatment effect at 12 weeks. The model will adjust for baseline value and stratification/minimisation covariates, plus other variables that are considered to be of prognostic importance. We will formally assess the distribution of the continuous outcome for evidence of departure from normality. If necessary, data will either be transformed or analysed using a non-parametric equivalent. Binary outcome (proportion achieving remission): Multiple logistic regression will be adopted to analyse binary outcomes. The model will test for an intervention effect after adjustment for the other intervention, stratification/minimisation variables and known prognostic factors. Secondary analyses will include multiple logistic regression to explore the possible gene-treatment interaction on remission rates.

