#### 3.1. Outcome measures

**3.1.1. Primary outcome measure:** The primary outcome measure is improvement in depressive symptoms at 12 weeks from the date of randomisation using the Quick Inventory of Depressive Symptomatology, self-report version [QIDS-SR16].

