### 9.2. Number of participants

The primary outcome is the level of depressive symptoms, measured using the QIDS-SR16. For comparisons of treatment groups at the margins as detailed in section 2.1, a minimum total sample size of 236 randomised participants (59 per arm) is required to detect a clinically important treatment effect on this outcome. This assumes a 20% loss to follow-up. Sample size has been calculated for the principal comparison for the primary outcome measure, the effect of lamotrigine on the primary outcome. A power of 90%, a 5% level of statistical significance, use of two-sided statistical tests throughout and an equal allocation to each arm have been assumed.

*9.2.1. Main effect of lamotrigine on primary outcome:* An absolute difference of 2 points on the QIDS score between Quetiapine+Placebo and Quetiapine+Lamotrigine is considered to be clinically important. From previous data, it has been estimated that the standard deviation of the QIDS in this population is 5.4. In order to detect this standardised difference of 0.37, a total of 186 randomised patients are required. This assumes a repeated measures analysis with 3 time points and a correlation between time points of 0.4. Allowing for a 20% loss to follow-up this increases to 236.

*9.2.2. Main effect of folic acid on primary outcome:* There is currently no QIDS-SR16 data available to assess the effect of folic acid. However, a total sample size of 186 gives the following power for a given effect size:

Effect size	Power
0.2	42%
0.25	60%
0.3	75%
0.35	87%

**9.2.3. Gene-treatment interaction (MTHFR C677T), (COMT Val158Met) and (FOLH1 T484C):** There are currently no QIDS-SR16 data available in the effect of treatment by genes. Therefore, we will conduct an exploratory analysis of the possible interactions between the genes MTHFR C677T, COMT Val158Met or FOLH1 T484C and response to treatment with folic acid.

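### Section 9.1 makes the primary mixed model conditional on the outcome's distribution and allows a switch that can abandon the raw-scale week-12 QIDS difference on which the trial is sized

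*Protocol*

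**What the plan says.** Section 3.1.1 defines the outcome: "The primary outcome measure is improvement in depressive symptoms at 12 weeks from the date of randomisation", measured by QIDS-SR16.

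Section 9.1 then describes the analysis.

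- The model is introduced conditionally: "Depending on the distribution of the continuous outcome measures, if appropriate, a mixed effect model will be used".
- The week-12 estimate comes from within that model: "Treatment-time interaction will be included in the model to assess the treatment effect at 12 weeks".
- The adjustment is broad: "The model will adjust for baseline value and stratification/minimisation covariates, plus other variables that are considered to be of prognostic importance". Section 3.2.3 lists 16 minimisation variables.
- The check is "We will formally assess the distribution of the continuous outcome for evidence of departure from normality", and the consequence is "If necessary, data will either be transformed or analysed using a non-parametric equivalent".
- The reporting commitment is "The results from the trial will be presented as comparative summary statistics with 95% confidence intervals".

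Section 9.2.1 sets the target on the raw scale: "An absolute difference of 2 points on the QIDS score between Quetiapine+Placebo and Quetiapine+Lamotrigine is considered to be clinically important". It takes an SD of 5.4 and a repeated measures analysis with 3 time points correlated at 0.4.

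Nothing elsewhere in the protocol says that the raw-scale estimate remains primary if the distribution check fails.

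**The concern.** The protocol states a rule under which the form of the primary analysis follows from the observed outcome data. Three features make it a poor rule.

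1. **It checks the wrong object.** A linear mixed model makes its distributional assumption about residuals and random effects. The distribution of the raw outcome also reflects treatment, baseline severity and the other covariates.
2. **It reacts to something of limited importance here.** With some 93 per side, a difference in means and its confidence interval are robust to moderate non-normality. A formal check can fail when the planned analysis is still sound.
3. **Its remedies change what is estimated.** Transformation moves the effect off the QIDS scale. A simple non-parametric test also gives up some or all of the structure that section 9.1 has just set out.

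At stake are the link between the primary result and the 2-point difference called clinically important and, depending on the method chosen, some power.

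**Working it through.** **Inputs from section 9.2:** difference 2 points, SD 5.4, standardised difference 0.37, two-sided 5%, power 90%, 3 time points, correlation 0.4, 186 participants before and 236 after allowance for 20% loss.

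**Assumed, not in the protocol:** a baseline to week-12 correlation of 0.4 (the protocol's 0.4 is between time points in its sample-size calculation), rank-test efficiency of 0.955 (its value for normal data), a QIDS range of 0 to 27, and the week-12 means used below.

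**1. The protocol's own figure.** The variance factor for the mean of three ratings is (1 + 2 × 0.4)/3 = 0.60. Then n per side = 2 × (1.960 + 1.282)² × 0.60 / 0.37² = 92.1, rounded up to 93, or 186 in total. Dividing by 0.8 gives 233, and the stated 236 is 4 × 59. The figure reproduces, but only for a raw-scale repeated-measures analysis.

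**2. Power at 93 per side,** from Φ(d × √(93 / (2v)) − 1.96) with d = 2/5.4 and v the variance factor.

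| Analysis | v | Power |
|---|---|---|
| Repeated measures as in 9.2.1 | 0.60 | 90% |
| Week 12, adjusted for baseline, r = 0.4 | 1 − 0.16 = 0.84 | 79% |
| Week 12, unadjusted t-test | 1 | 71% |
| Week 12, unadjusted rank test | 1/0.955 | 69% |

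The 0.60 factor is the variance of an average over three ratings, so the like-for-like comparison at week 12 is 69% against 79%. Of that gap, 8 points come from dropping baseline (79% to 71%) and only 2 from using ranks (71% to 69%).

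**3. An adjusted rank method.** For rank analysis of covariance under normality with r = 0.4 (rank correlation 0.385), relative efficiency is 0.955 × 0.84 / (1 − 0.385²) = 0.942. Power is then Φ(0.370 × √(93 × 0.942 / (2 × 0.84)) − 1.96), about 76% against 79%.

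**4. Scale.** On a ratio scale, as after a log transformation, 2 points corresponds to 4/6 = 0.67 at a control mean of 6, 8/10 = 0.80 at 10 and 12/14 = 0.86 at 14. Conversely, a ratio of 0.80 corresponds to 1.2 points at a mean of 6 and 2.8 points at 14. No single ratio stands for 2 QIDS points.

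**5. Whether the switch would be triggered.** 4,000 simulated trials per setting, 93 per side, used normal scores with SD 5.4 and means 2 points apart, rounded and truncated to 0–27. The table shows how often a Shapiro-Wilk test at 5% rejects, with the power of the two unadjusted tests.

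| Control mean | Pooled outcome | Within-arm residuals | t-test power | Rank-test power |
|---|---|---|---|---|
| 7 | 100% | 100% | 70% | 69% |
| 9 | 100% | 93% | 69% | 68% |
| 11 | 77% | 35% | 71% | 69% |
| 13 | 18% | 10% | 69% | 67% |

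The trigger rate depends heavily on the assumed mean. At every setting the t-test did at least as well as the rank test, so abandoning the mean difference would have gained nothing.

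**The case against.** Several stronger readings are tempting, and the protocol does not support them.

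- **That the fallback must lose the covariates and repeated measures.** Transformation is the first option named, and a transformed score can go into the same mixed model with baseline, covariates, repeated ratings and incomplete follow-up all retained. Only the scale changes.
- **That no non-parametric method could serve.** Section 9.1 does not specify an unadjusted rank test. Rank analysis of covariance adjusts for baseline, rank methods for repeated measures handle group-by-time effects, and median regression adjusts and reports in QIDS points. None gives the planned adjusted mean difference, but the power loss could be small, as step 3 shows.
- **That the switch is likely.** The protocol gives no week-12 mean or distribution, and it does not say that the formal assessment is a 5% significance test.
- **That the analysis could be picked by its result.** The text does not say that the check uses allocation, and section 5.9 maintains masking during the trial. A pooled, blinded check is compatible with it. In simulation at a control mean of 9, free choice among t-test, log t-test and rank test raised type I error from about 5% to 7.4%, but that is a worst case and not the stated rule.
- **That a rank test would lose a further 20%.** The 93 per side is already net of that loss (236 × 0.8 = 188.8). A mixed model can use earlier ratings from people without a week-12 rating, but that gain has not been quantified.

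The choice of test, threshold, transformation and timing commonly belongs in the statistical analysis plan, so their absence is not the point. What stands is the rule itself: the protocol makes its primary model conditional and does not keep the raw-scale estimate primary.

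**Conclusion.** The point holds in a limited form and should be corrected. Section 9.1 lets a check of the outcome's distribution displace the planned adjusted week-12 difference. Either remedy can separate the primary result from the 2-point raw-scale target in section 9.2.1, and a simple non-parametric test would also give up some or all of the planned structure.

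The certain cost is to interpretation, because a transformed analysis does not estimate a fixed number of QIDS points. The power cost depends on the method chosen. It is about 10 percentage points (79% to 69%) if the fallback were an unadjusted week-12 rank test and baseline correlates 0.4 with week 12, and about 3 points for a baseline-adjusted rank method. Both figures use the rank efficiency that applies to normal data.

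A reader might infer that the sample size is wrong. It is not: 186 reproduces for the raw-scale repeated-measures analysis assumed.

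**What to change.** In section 9.1, for the primary outcome:

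1. Delete the condition on distribution and appropriateness that introduces the mixed model, and the sentence "If necessary, data will either be transformed or analysed using a non-parametric equivalent".
2. State that the primary result for each marginal comparison is the week-12 treatment difference from the adjusted mixed model on untransformed QIDS-SR16, with its 95% confidence interval, whatever the distribution.
3. Direct the diagnostic check at the model residuals. Report robust or bootstrap standard errors, and any transformed or rank-based analysis, only as sensitivity or supplementary results.

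This changes a few sentences and leaves the sample size and data collection as they are. The downside is small: some efficiency could be lost if the residuals were markedly non-normal, and the supplementary analyses would show whether the conclusion depends on that.

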**3.1.2. Secondary outcome measures:**

1. The proportion of participants who both achieve remission by 12 weeks following randomisation (defined as a score of  $\leq 5$  on QIDS-SR16) and remain free from symptomatic relapse by 52 weeks. Depressive relapse is defined as a QIDS-SR16 score  $\geq 10$  on two consecutive weekly ratings and manic relapse as an Altman Self-Rating Mania Scale (ASRM) score of  $\geq 10$  on a single weekly rating.
2. Proportion of time over 12 months when participants were free from manic symptoms (ASRM  $\leq 5$ ).
3. Proportion of time over 12 months when participants were free from depressive symptoms (QIDS-SR16  $\leq 5$ ).
4. New intervention (admission or drug treatment) for manic episode by 52 weeks.
5. New intervention (admission or drug treatment) for depressive episode by 52 weeks.
6. Death (all cause and cause-specific including suicide).
7. Deliberate self-harm.
8. Quality of life – rated using the EuroQol EQ-5D.
9. Unexpected adverse events.
10. Withdrawal from quetiapine or lamotrigine due to adverse effects.
11. Use of health and social care service resources.
12. Social costs/benefits.

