### 5.6. Participant reported outcomes

Participants will be asked to complete the QIDS-SR16 and the ASRM rating scales by SMS (or webform or hardcopy) once a week for the duration of the randomised phase (see section 5.7. for procedures). In addition to this, participants will be asked, once a month, to complete the EuroQol scale and report contact with health and

social care professionals and initiation of new treatment for mood symptoms. If either contact or new treatment is reported, a member of the CEQUEL team will phone or email the participant to collect further information.

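### Logistic regression appears to cover the two new-intervention outcomes that accumulate to 52 weeks; a time-to-event analysis would use time at risk and avoid an arbitrary coding of lost participants

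*Protocol*

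**What the plan says.** Section 3.1.2 lists as secondary outcome 4 "New intervention (admission or drug treatment) for manic episode by 52 weeks" and as outcome 5 "New intervention (admission or drug treatment) for depressive episode by 52 weeks".

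Section 9.1 describes a mixed model for continuous outcomes and then turns to yes/no outcomes. The label reads "Binary outcome (proportion achieving remission", and the sentence that follows is general: "Multiple logistic regression will be adopted to analyse binary outcomes". The model adjusts for the other intervention, the minimisation variables and known prognostic factors. The section names no time-to-event method.

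Loss appears in section 9.2, in the sample size for the primary outcome: "This assumes a 20% loss to follow-up". It is not split by arm, and no separate figure is given for 52 weeks.

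Event information comes from several sources. Section 5.6 has participants report monthly on contacts with services and on "initiation of new treatment for mood symptoms", followed by a call or email from the trial team. Sections 5.3.1, 5.4.1 and 5.5.1 collect admissions and new treatments from investigators at 12, 22 and 52 weeks.

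**The concern.** Outcomes 4 and 5 are cumulative over a year. Someone last seen in week 20 without an event was at risk for 20 weeks, but has no yes/no answer at week 52. Logistic regression needs that answer, so the analyst must choose one of three codings:

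- **A:** count lost participants without an event as event-free.
- **B:** drop lost participants without an event, but keep those whose event was seen before loss.
- **C:** drop everyone lost before week 52, including those with a recorded event.

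A and B err in opposite directions when loss differs between arms, so the same data could lean towards either arm. C discards observed events and time at risk. Section 3 names prevention of depressive or manic relapse among the things the trial investigates, and these outcomes measure it through treatment actions. The choice therefore bears on the long-term conclusions, though not on the primary analysis.

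**Working it through.** **1. The plan's own figure, to place the 20%.** Section 9.2.1 gives a 2-point difference, SD 5.4 (standardised 0.37), three time points and correlation 0.4. Section 9.2 gives "A power of 90%, a 5% level of statistical significance, use of two-sided statistical tests throughout and an equal allocation to each arm". The variance factor is (1 + 2 × 0.4)/3 = 0.6. Per group, n = 2 × (1.960 + 1.282)² × 0.6 / 0.37² ≈ 92.1, so 93, or 186 in total. Then 186/0.8 = 232.5, so 233, which becomes 236 as 4 × 59. The stated 186 and 236 reproduce. The 20% is thus an inflation for the primary QIDS outcome. Each marginal comparison has 118 per group.

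**2. Model for outcomes 4 and 5.** The documents give neither a 52-week event rate nor loss by arm, so the following are assumptions:

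- 118 per group and the same event rate r in both groups (no true effect);
- exponential event times and independent exponential loss times;
- loss d of 20/20, 15/25 or 10/30%, averaging the protocol's 20%.

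With one year as the time unit, λ = −ln(1 − r) and μ = −ln(1 − d):

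- event seen before loss: E = λ/(λ+μ) × (1 − exp(−(λ+μ)));
- followed to week 52 without an event: S = exp(−(λ+μ)).

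Coding A compares E between groups; coding B compares E/(E+S).

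**3. One case in full: r = 40%, loss 10% versus 30%.** λ = 0.511; μ = 0.105 and 0.357.

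- A: 38.1% versus 34.2%. Odds ratio (heavier-loss over lighter-loss arm) 0.84.
- B: 41.4% versus 44.8%. Odds ratio 1.15.

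**4. Range.** Odds ratios are heavier-loss over lighter-loss arm. Rejection rates are two-sided at 5%, by normal approximation; the true odds ratio is 1.

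| Event rate | Loss | A: OR (rejection) | B: OR (rejection) |
|---|---|---|---|
| 10-50% | 20/20 | 1.00 (5.0%) | 1.00 (5.0%) |
| 10% | 10/30 | 0.88 (5.9%) | 1.14 (5.9%) |
| 20% | 15/25 | 0.93 (5.5%) | 1.07 (5.4%) |
| 20% | 10/30 | 0.87 (7.0%) | 1.14 (6.7%) |
| 40% | 15/25 | 0.92 (6.2%) | 1.07 (5.7%) |
| 40% | 10/30 | 0.84 (9.8%) | 1.15 (7.8%) |
| 50% | 15/25 | 0.91 (6.6%) | 1.08 (5.7%) |
| 50% | 10/30 | 0.82 (11.6%) | 1.16 (8.0%) |

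In simulation (6,000 runs) at 40% and 50% events with 10/30 loss, the log-rank test rejected in 5.0% and 5.2% of runs. Coding C rejected in 5.2% and 4.9%, so it is unbiased here.

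**5. Power with a real effect.** Hazard ratio 0.6, equal 20% loss, control event rate 40% or 50%:

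- log-rank (simulation): 57% and 67%;
- coding C (simulation): 51% and 60%, a cost of about 6 to 7 points;
- coding A (normal approximation): 55% and 65%, a cost of about 2 points.

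**The case against.** The case against has five parts.

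- **Assignment.** Section 9.1 never names outcomes 4 and 5, and its label mentions only remission. That stands: the assignment is an inference. It is the natural one, because the sentence is general and no other method in 9.1 fits a yes/no event.
- **SAP content.** The coding rule for lost participants is ordinary SAP material, and no SAP is shown. That stands too, so the absence of a rule is not the point here. What the protocol does name is a method that ignores time at risk, and an SAP following it would still face participants with no week-52 status.
- **Loss.** A reader might infer that the assumed 20% loss will itself produce a spurious treatment effect. The documents do not support this. The 20% belongs to the primary outcome, and equal, independent loss gives an odds ratio of 1.00. The trial is double-blind with a run-in. Follow-up continues after treatment stops unless consent is withdrawn (5.13), telephone follow-up is planned (3.2.4), and the 22-week form can be completed without the participant (5.4). Loss for these events may be below 20%.
- **Event rates.** Those of 40-50% may not suit the manic outcome. The only related figures are 2.2-3.9% (hypo)mania in the 8-week quetiapine trials (1.3.1). At an assumed 10% rate, the error rate stays near 6% even at 10/30 loss. For the depressive outcome, a constant hazard ignores the request in 6.5.6 not to add depression treatment in the first 12 weeks.
- **Remedy.** Censoring is itself biased if people who are deteriorating leave. That stands; the proposed analysis does not cure informative dropout.

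**Conclusion.** The point holds as a modest improvement to two secondary outcomes. The only method stated for yes/no outcomes does not use time at risk. Applied to outcomes 4 and 5, it forces a coding choice that can reverse the direction of the estimate when loss is unequal.

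Under the assumptions above, the distortion is small at 15% versus 25% loss (odds ratio 0.91-0.93 or 1.07-1.08 for event rates of 20-50%). It is larger at 10% versus 30% (0.82-0.84 or 1.15-1.16 at 40-50% event rates). It is absent with equal, independent loss, and the error rate is little inflated when events are rare. Dropping everyone lost avoids bias under independent loss but gives up about 6-7 points of power in the case shown.

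Event rates, loss splits and exponential times are assumptions, so these are illustrative ranges and not expected effects. The primary outcome is not affected.

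**What to change.** In section 9.1, add that outcomes 4 and 5 are analysed as time from randomisation to first new intervention:

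- Kaplan-Meier curves by group, and a Cox model including the other intervention and key baseline factors;
- censoring at the last contact at which event status is known, from participant or investigator;
- the 52-week Kaplan-Meier risk difference with 95% CI, which keeps the outcome as defined in 3.1.2.

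Record the start date of each new treatment or admission on the existing 12-, 22- and 52-week forms and in the calls that follow monthly reports. Keep logistic regression for outcomes fixed at one time point.

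The cost is a short addition to 9.1 and one date field. The analysis assumes loss is non-informative given the covariates, and this should be stated with the result.
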